13.1.1 CENTRAL CORNEAL STAINING SCORE (CCSS)

CCSS CFB to Day 57 will be analyzed using the ITT population with multiple imputation methodology specified in Estimand 1 ([Section 2.6](#)). The initial MMRM model will include terms for baseline CCSS, site, visit (as categorical term), treatment group and the interaction of treatment group and visit as fixed effects with correlated errors. The inclusion of site in the final model will be evaluated at an alpha level of 0.1. All post-baseline visits will be used in the model.

If site is retained in the final primary analyses, the site by treatment interaction will be explored in a separate analysis to evaluate how the treatment effect may differ across sites. All post-baseline visits will be used in the model.

An alternate MMRM will be executed as supportive analysis. This additional model will include all terms in the final model of the primary analyses with, [REDACTED]

Sensitivity analyses to compare CCSS CFB between treatment groups using imputation by Last Observation Carried Forward (LOCF), multiple imputation by placebo group-based pattern mixture models (PMM), and analyses of observed data only using the ITT and PP populations will be conducted.

The Least Square (LS) means, LS mean difference, Standard Errors (SEs), two-sided 95% CIs, and p-values of the LS mean difference will be reported from the MMRM model. Two-sample t-tests will also be conducted as supportive analyses of the mean CFB to Day 57. The sample means, sample mean difference, SEs, two-sided 95% CIs, and two-sided p-values will be reported from the two-sample t-test.

The MMRM LS means of the CCSS CFB in the study eye at Day 57 and CCSS CFB at each visit will be displayed graphically in a bar chart with SE bars by treatment group.

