13.2.1 ANALYSES OF SECONDARY ENDPOINTS

Actual scores will be summarized by visit and region/symptom using quantitative summary statistics. Two-sample t-tests will be employed to compare active treatment and placebo means of actual scores at each visit. The differences in samples means, SEs, two-sided 95% CIs for the difference in means and p-values will be reported.

Changes from baseline at each post-baseline visit will be summarized similarly. Analysis of the change from baseline at each post-baseline visit will utilize MMRM models similar to the primary analysis (substituting appropriate baseline and week variables) using observed data. The LS means, LS mean differences, SEs, two-sided 95% CIs for the difference in means and two-sided p-values will be reported from the models. Two sample t-tests will also be conducted. Within each treatment arm, paired t-tests will be conducted for changes from baseline. Analyses will be performed on the ITT population with observed data only. For assessments on both eyes, only the study eye will be analyzed and summarized.

Subject listings of each secondary efficacy assessment will be generated.

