PROC MIXED DATA = OUTDATA;
    BY _IMPUTATION_;
    CLASS TREATMENT;
    [REDACTED]
    COVB;
    LSMEANS TREATMENT / CL PDIFF;
    ODS OUTPUT LSMEANS = OUTLS DIFFS = OUTDIFFS;
    RUN;

    PROC SORT DATA=OUTLS; BY TREATMENT _IMPUTATION_; RUN;

    PROC MIANALYZE DATA=OUTLS;
        BY TREATMENT;
        MODELEFFECTS ESTIMATE;
        STDERR STDERR;
    RUN;

    PROC SORT DATA=OUTDIFFS; BY _IMPUTATION_; RUN;

    PROC MIANALYZE DATA=OUTDIFFS;
        MODELEFFECTS ESTIMATE;
        STDERR STDERR;
    RUN;
```

where

- TREATMENT is the name of the treatment group variable
- SITE is the study site id as a random effect

- BASELINE is the baseline CCSS in the study eye
- CFB is the change from baseline in CCSS in the study eye at Day 57
- OUTLS is the name of the output dataset that contains the statistical results for the treatment mean from the MMRM model that is run on each of the twenty imputation datasets
- OUTDIFFS is the name of the output dataset that contains the statistical results for the difference in treatment mean from the MMRM model that is run on each of the twenty imputation datasets

Similar SAS® code will be used to conduct MCMC multiple imputation analysis for the two sample t-test.

Furthermore, the SAS® code for obtaining the placebo-based PMM imputation data is:

```

PROC MI DATA = INDATA SEED = 988416 OUT = MDATA NIMPUTE = 30
  MINIMUM = 0 MAXIMUM = 4 ROUND = 0.5;
  MCMC IMPUTE=MONOTONE;
  VAR BASE V3 V4 V5 V6;
RUN;

PROC MI DATA = MDATA SEED = 253464 OUT = OUTDATA NIMPUTE = 1
  MINIMUM = . 0 0 0 0
  MAXIMUM = . 4 4 4 4
  ROUND = . 0.5 0.5 0.5 0.5;
  CLASS TREATMENT;
  MONOTONE REG(V6 = V5 V4 V3 BASE / DETAILS);
  MONOTONE REG(V5 = V4 V3 BASE / DETAILS);
  MONOTONE REG(V4 = V3 BASE / DETAILS);
  MONOTONE REG(V3 = BASE / DETAILS);
  MNAR MODEL(BASE V3 V4 V5 V6/ MODELOBS=(TREATMENT='Placebo'));
  VAR TREATMENT BASE V3 V4 V5 V6;
RUN;

```

where

- INDATA is the name of the input dataset
- MDATA is the name an intermediary dataset with a monotone missing pattern
- OUTDATA is the name of the output dataset
- TREATMENT is the name of the treatment group variable
- BASE is the baseline CCSS in the study eye
- V3 – V6 is the CCSS in the study eye at Visit 3 through Visit 6

An example of the SAS® code implementation of the MMRM model for the observed data only is as follows:

```
PROC MIXED;
```

Protocol HL036-DED-US-P302 SAP, Version 1.0

```
CLASS PATIENT WEEK TREATMENT;  
MODEL CFB = WEEK BASELINE TREATMENT / SOLUTION COVB;  

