[REDACTED]  
LSMEANS TREATMENT / CL PDIFF;  
RUN;
```

25. Appendix 2

Schedule of Visits and Assessments

Procedure	Screening Visit 1 (Day -14 ± 2)	Baseline Visit 2 (Day 1)	Visit 3 (Day 8 ± 1)	Visit 4 (Day 15 ± 2)	Visit 5 (Day 29 ± 2)	Visit 6 (Day 57 ± 3)	Visit 7-9 ⁴
Informed Consent / HIPAA	X						
Medical / Medication History and Demographics	X						
Placebo Run-In Collection		X					
Study Drug Collection			X	X	X	X	
Medical / Medication Update		X	X	X	X	X	X
Pregnancy Test	X ²					X ²	
Ocular Discomfort Scale	X	X	X	X	X	X	
Ocular Discomfort & 4-Symptom Questionnaire	X	X	X	X	X	X	
VAS	X	X	X	X	X	X	
OSDI® Questionnaire	X	X	X	X	X	X	
Visual Acuity (ETDRS)	X	X	X	X	X	X	
Slit Lamp Biomicroscopy	X	X	X	X	X	X	
Conjunctival Redness	X	X	X	X	X	X	
TFBUT	X	X	X	X	X	X	
Fluorescein Stainng	X	X	X	X	X	X	
Lissamine Green Staining	X	X	X	X	X	X	
Schirmer's Test	X	X		X	X	X	
Intraocular Pressure	X					X	
Dilated Fundus Exam	X					X	
Review of Qualification Criteria	X	X					

Placebo Run-In Dispensation and Instillation	X						
Blood Sampling for Immunogenicity		X			X	X	X
Randomization		X					
Study Drug Instillation		X	X				
Drop Comfort Scale		X	X				
Drop Comfort Questionnaire		X	X				
Adverse Event Query	X	X	X	X	X	X	X
Study Drug Dispensation		X ¹	X	X	X		
Exit Subject from Study						X ³	

¹ The Visit 2 study drug kit is re-dispensed at Visit 3 (as each kit includes 2-week supply of study drug).

² To women of child-bearing potential.

³ For subjects with negative immunogenicity results at Visit 6.

⁴ Subjects will be asked to return for Blood Sample for Immunogenicity Testing if they test positive for immunogenicity at Visit 6. Visit 7 will occur approximately 6-12 months after Visit 6. If subject tests positive for immunogenicity at Visit 7, they will be asked to return for Visit 8 approximately 12 months after Visit 7. If subject tests positive for immunogenicity at Visit 8, subject will be asked to return for Visit 9 approximately 12 months after Visit 8.

Certificate Of Completion

Envelope Id: 0FD96C8D49AC44D78A4A23EF3B2091D1 Status: Completed

Subject: Complete with DocuSign: HanAll HL036-DED-US-P302 Statistical Analysis Plan Draft V1.0 23-JAN-20...

Source Envelope:

[figure not shown]
Document Pages: 45 Signatures: 3

Certificate Pages: 5 Initials: 0

AutoNav: Enabled

Enveloped Stamping: Disabled

Time Zone: (UTC-05:00) Eastern Time (US & Canada)

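### The observed-data MMRM example in SAP Appendix 1 omits the treatment-by-visit interaction, so run as written it would put an all-visit effect into four sensitivity tables titled as Day 57 results

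*SAP*

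**What the plan says.** **The example.** SAP Section 24, Appendix 1, ends with a block introduced as an example of the "code implementation of the MMRM model for the observed data only is as follows". It declares patient, week and treatment as class variables. Its model statement is "MODEL CFB = WEEK BASELINE TREATMENT / SOLUTION COVB", closed by a semicolon. A redacted line follows, then "LSMEANS TREATMENT / CL PDIFF". This is the only observed-data MMRM code in the SAP.

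**The governing text.**
- SAP 13.1.1 lists, among the terms of the primary model, "treatment group and the interaction of treatment group and visit as fixed effects with correlated errors". It uses all post-baseline visits and plans a display of "The MMRM LS means of the CCSS CFB in the study eye at Day 57 and CCSS CFB at each visit". It also plans observed-data sensitivity analyses in the ITT and PP populations.
- SAP 13.1.2 applies the same analysis to EDS, with baseline EDS as covariate.
- SAP 13.2.1, for the secondary endpoints on observed data, states: "Analysis of the change from baseline at each post-baseline visit will utilize MMRM models similar to the primary analysis".
- The protocol 10.4.5 code uses `VISIT|TREATMENT` and requests LS means for `TREATMENT*VISIT`. Protocol 10.4.6 names the interaction for the secondary endpoints.
- SAP Section 18 declares no change from the protocol's analyses.

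**The concern.** The example and the text describe different models. The text allows the treatment effect to differ by visit and reads off the Day 57 contrast. The example allows a single treatment effect and requests a single contrast.

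SAP Section 21 lists four primary-endpoint tables on observed data: 14.2.1.6 (CCSS, ITT), 14.2.1.7 (CCSS, PP), 14.2.2.5 (EDS, ITT) and 14.2.2.6 (EDS, PP). All four titles give Visit 6 (Day 57). If a programmer ran the example as it stands, each would report an effect pooled over visits, and nothing in the output would flag it. These tables are meant to check the robustness of the Day 57 result, and they would estimate something else.

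In the by-visit secondary tables (14.2.3 to 14.2.11) the same code would fail openly, because the visit contrasts could not be produced.

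**Working it through.** No figure in the plan needs reproducing. The check compares the two specifications and then works out what the example estimates.

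**1. Does the example contain the interaction?** The model statement has three terms (week, baseline, treatment) and is closed before the redacted line, so the hidden line cannot add a fixed effect to it. The LSMEANS request is visible and names treatment alone.

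**2. What does it estimate?** With complete data and a common covariance matrix S across arms, the treatment coefficient of the additive model is a weighted mean of the visit effects d:

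all-visit effect = w′d, with w = S⁻¹1 / (1′S⁻¹1).

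Under compound symmetry with four visits, each weight is 0.25.

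**3. Effect relative to Day 57.** The documents do not give the inputs, so the profiles (Visits 3, 4, 5, 6, with Day 57 = 1) and the correlations of 0.3 to 0.7 are assumptions. The last column uses AR(1) with SDs rising 0.7, 0.8, 0.9, 1.0.

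| Assumed profile | Compound symmetry | AR(1) | AR(1), rising SD |
|---|---|---|---|
| Constant: 1, 1, 1, 1 | 1.00 | 1.00 | 1.00 |
| Ramp: 0.25, 0.5, 0.75, 1 | 2.5/4 = 0.625 | 0.625 | 0.45–0.53 |
| Late: 0, 0, 0.5, 1 | 1.5/4 = 0.375 | 0.40–0.44 | 0.22–0.27 |
| Fading: 1.5, 1.4, 1.2, 1 | 5.1/4 = 1.275 | 1.26–1.27 | 1.33–1.38 |

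**4. Standard error relative to Day 57.** Under compound symmetry the ratio is √((1 + 3ρ)/4):
- ρ = 0.3: √0.475 = 0.69
- ρ = 0.5: √0.625 = 0.79
- ρ = 0.7: √0.775 = 0.88

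**5. Effect on the test statistic.** The ratio of expected z values is the effect ratio divided by the SE ratio. At ρ = 0.5 it is 1/0.791 = 1.26 for a constant effect and 0.625/0.791 = 0.79 for the ramp. The pooled result can therefore look stronger or weaker than the Day 57 result.

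**6. Simulation check.** 300 runs with 135 per arm, compound symmetry, ρ = 0.5, the ramp profile and a Day 57 effect of −0.500 SD. The additive model averaged −0.310 (formula: 0.625 × −0.500 = −0.3125). The Week 8 difference averaged −0.496.

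**The case against.** **The text already settles it.** SAP 13.1.1 states the interaction, the code is only labelled an example, and the example is assigned to no table. The SAP's precedence over the protocol changes nothing, since the SAP's own text has the right model. All of this stands and is why the point is minor. It does not remove the contradiction: the one piece of code offered for these analyses gives a different quantity from the one the text specifies.

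**The input might be Day 57 only.** The example names no dataset, and the only definition of CFB in Appendix 1, in the imputed-data block, is the change at Day 57. The multi-visit reading is therefore an inference. It is the natural one: week is both a class variable and a model term, which would be pointless with one visit, and 13.1.1 uses all post-baseline visits. If the input were restricted to Day 57, the code would not be the MMRM its label claims.

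**A reader might infer that the primary analysis is affected**, because the imputed-data block also requests LS means for treatment alone. The documents do not show this. That block's model line is redacted and its CFB is defined at Day 57.

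**A reader might also infer the size and direction for CCSS** from the earlier Phase 3 study in protocol Section 1 (p = 0.048 at Week 1, p = 0.024 at Week 8): little bias, and tables that look firmer than the Day 57 result. Those p-values cannot carry this. Taken as z = 1.977 and 2.257 with equal standard errors, their ratio is 0.88, but its 80% Fieller interval is 0.38 to 1.73 (assumed correlation 0.5). No Week 2 or Week 4 result is given. At a ratio of 0.38 with a linear-by-day course (0.38, 0.47, 0.65, 1; mean 0.62), the z ratio at ρ = 0.5 is 0.62/0.79 = 0.78, so the result would look weaker.

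**Conclusion.** The inconsistency is real and explicit against SAP 13.1.1. Against 13.2.1 it follows from the call for results at each visit, since that section does not itself name the interaction. The text is right and the example is the outlier.

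The all-visit effect matches Day 57 only under a constant treatment effect. Beyond that, the size and direction of any difference are unknown, and the ratios above illustrate assumed profiles and covariances only. That the four tables would be affected assumes the example is run literally on all post-baseline visits.

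Severity is minor. The four tables are sensitivity analyses, the secondary analyses are hypothesis-generating (SAP 8.5), and the plan keeps an independent Day 57 check: "Two-sample t-tests will also be conducted as supportive analyses of the mean CFB to Day 57".

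**What to change.** In the observed-data example in Appendix 1:
- add `WEEK*TREATMENT` to the MODEL statement;
- request `LSMEANS WEEK*TREATMENT / CL PDIFF`;
- state that the Week 8 contrast is the one reported in Tables 14.2.1.6, 14.2.1.7, 14.2.2.5 and 14.2.2.6;
- state that each visit's contrast is reported for the secondary endpoints (three post-baseline visits for Schirmer's test, four for the others).

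The cost is an edit to one code example. Data, design and the stated analyses do not change.
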